Box 2. Summary of study methods

	matched on birth-year. This date will be the non-initiator comparators index-date . Thus, with regards to treatment, the active treatment arms initiate a treatment on index-date and non-initiator comparators do not.
Outcome	First recorded occurrence of SD, including the following ICD-10 codes: F52.0, F52.1, F52.2, F52.3, F52.6, F52.8, F52.9, N48.4, N94.1, N48.3 [See section 4.6, Outcome]
Follow-up	Patients will be followed-up from index-date up to maximum 1 year. Thus, patients will be followed-up from index-date to the earliest of: date of first occurrence of outcome, loss to follow-up, death (only available in IMRD UK), end of follow-up (1 year) or end of the study period [See Section 4.5, Follow-up period]
Casual contrast of interest	Intention to treat effect, i.e., patients were followed up irrespective of treatment change (main analysis).
Statistical methods	
• Inverse probability of treatment weighting (IPTW) will be used to adjust for confounders measured at cohort entry.• Incidence rates (IR) and cumulative incidence proportions will be estimated for each treatment cohort.• Hazard ratios (HRs) will be estimated using a Cox proportional hazards model.• Cumulative incidence proportions will be estimated for each treatment arm using the Kaplan-Meier estimator.• Sensitivity analyses will include a "Per-protocol" analytical strategy and adjusting for informative censoring at treatment protocol violation. 
[See Section 4.7. Statistical analyses]

115

116

117 4.1. Study design

118 Comparative cohort design, including:

119 a) Active comparator, new user design:

120 • Esomeprazole initiators (target treatment [Cohort 1]) will be compared to the following
121 comparators: pantoprazole [Cohort 3], lansoprazole [Cohort 4], and H2RAs [Cohort 5]
122 initiators.

123 • Omeprazole initiators (target treatment [Cohort 2]) will be compared to the following
124 comparators: pantoprazole [Cohort 3], lansoprazole [Cohort 4], and H2RAs [Cohort 5]
125 initiators.

126 Treatment initiation will be defined as the prescription date for PPIs/H2RAs after a washout
127 window of at least 365 days in which no previous prescription with any PPIs or H2RAs have
128 been recorded. This date will coincide with the cohort entry or start of follow-up in the study,
129 which we will refer to as **index-date**.

130 b) Non-initiator comparator

[figure not shown]

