174 ¹ These indications are selected indications for PPIs and H2RAs. We restricted the study population to patients with
175 chronic indications, for which treatment is likely chronic. The rationale for this is explained in Limitations (first
176 paragraph)

177 ² These are assumed to be proxies of indications (e.g., PPIs are indicated to patients requiring continued NSAID or
178 antithrombotic therapy).

179

180 **4.4. Recruitment period**

181 The recruitment period will start on January 1st, 2005, and will end on December 31st 2020 in both
182 IQVIA™ DA Germany and IMRD UK.

183 Although the first use of esomeprazole dates to September 2000, in IMRD UK and October 2000, in
184 IQVIA™ DA Germany, we opted to include data from 2005 the year when the distribution of male
185 sexual dysfunction events started being consistent.

186 Additionally, we opted to limit the recruitment period up to 2020 because the use of H2RAs is very
187 limited in IQVIA™ DA Germany after 2020. Of note, the suspension of all ranitidine medicines in the
188 European Union due to the presence of low levels of an impurity called N-nitrosodimethylamine
189 (NDMA) in April, 2020^[1] led to the suspension of ranitidine, the dominant H2RA in Europe.

[figure not shown]
190

191 **4.5. Follow-up period**

192 Patients will be followed-up from index-date up to maximum one year. For instance, patients recruited
193 in 2020 can be followed up to 2021. Thus, patients will be followed-up from index-date to the earliest
194 of: date of first occurrence of outcome, loss to follow-up (e.g., transfer out date from the general
195 practice in IMRD or end of continuous observation of the patient by the practice in IQVIA™ DA
196 Germany, or date of last data collection from the practice), death (only available in IMRD UK), end of
197 follow-up (1 year) or end of the study period.

198 Considering the recommended duration for these treatments (4-8 weeks for PPIs and 8-12 weeks for
199 H2RAs), a patient may participate with several treatment episodes - and consequently index-dates -
200 during the study period. For example, a patient may receive a prescription for 8 weeks after which the
201 medication is discontinued to assess the need for ongoing therapy (on-demand or intermittent use).
202 After 15 months of discontinuing this therapy, the patient may receive another prescription for the
203 same therapy and duration. Therefore, this patient will enter the study twice and contribute with two

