 233 exposure) with any certainty. Electronic health records may not capture the entire patient
 234 history of utilisation of these treatments. In addition, these treatments are used
 235 interchangeably which would mean that a substantial number of individuals would be excluded
 236 from the study population if the study focuses only on first use ever of any of these
 237 substances. Therefore, the study will assess initiation of treatment after a washout window of
 238 at least 365 days.

239 Prescriptions will be identified through keyword searches using international non-proprietary
 240 names (INNs) in several prescription-related variables (e.g., "Therapy Name", "Product Name",
 241 "Molecule"). Detailed list of keywords used are provided in **Annex 2**.

242 PPIs will include the most prescribed substances in each database, i.e., esomeprazole,
 243 omeprazole, and pantoprazole in IQVIA™ DA Germany, and esomeprazole, omeprazole, and
 244 lansoprazole in IMRD UK. Other PPIs such as dexlansoprazole and rabeprazole are less
 245 commonly recorded in the selected databases and, therefore, will not be included in this study.

246 Products containing H2RAs will include the following substances (ordered by frequency of
 247 prescribing): ranitidine, famotidine, nizatidine, cimetidine in IMRD, and ranitidine, famotidine,
 248 cimetidine, nizatidine in IQVIA™ DA Germany.

249 **Annex 2** provides details on the use of PPI and H2RA substances over time in each database.

250

251 b) Non-initiators arm (cohort)

252 Non-initiator comparators will be randomly sampled and selected on each date of the
 253 recruitment period when esomeprazole/omeprazole initiators start treatment, **matched on**
 254 **birth-year**. This date will be the non-initiator comparators index-date. Thus, with regards to
 255 treatment, the active arms initiate a treatment on index-date and non-initiator comparators do
 256 not. Matching on index-date and on year of birth is meant to ensure a similar distribution of
 257 calendar time and age at index-date, both of which are considered important potential
 258 confounders.

259 It should be noted that *non-initiators* refer to patients who have selected indications (see Table
 260 1 above, inclusion criteria) recorded in the databases but who did not initiate therapy (i.e., did
 261 not have a recorded PPIs or H2RA prescription within 12 months before index-date or on index
 262 date).

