299 washout) esomeprazole versus patients who: a) initiated other proton pump inhibitors (PPIs, namely
300 omeprazole, pantoprazole/lansoprazole); b) initiated histamine type 2 receptor antagonists (H2RA))
301 and c) patients who did not initiate treatment with either PPIs or H2RA but had received a diagnostic
302 for a PPI or H2RA indication (i.e. non-initiators comparators). Outcome events will be attributed to the
303 baseline treatment protocol regardless of treatment change during follow-up. (i.e., **intention-to-treat
304 analysis (ITT)**).

305

306 4.7.2. Descriptive analysis

307 Descriptive analyses will be performed to describe the study cohorts at baseline in terms of
308 demographic characteristics, lifestyle factors, potential indications, comorbidities, and history of
309 treatment with drugs commonly associated with sexual dysfunction.

310

311 4.7.3. Main statistical analysis

312 **Inverse probability of treatment weighting (IPTW)**

313 Inverse probability of treatment weighting (IPTW) will be used to render the assignment of study
314 treatments independent of the baseline measured covariates, thus minimising the potential
315 confounding effect of these covariates.

316 Using IPTW, the average treatment effect (ATE) in the entire study population will be estimated,
317 assuming that all important confounding variables have been accounted for. For each observation in
318 the study population, the IPTW is the inverse of the probability of receiving the observed treatment

319 conditional on all variables considered sufficient for confounding adjustment. In order to stabilize the
320 weights (i.e., less extreme weights, that are closer to the mean weight of one), the numerator of one
321 will be replaced by the marginal probability of receiving the observed treatment in the study population
322 (i.e., the proportion of observations in the study population with the respective treatment). (Hernan &
323 Robins, 2006) All analyses will then be conducted in the re-weighted population without additional
324 confounding adjustment on the assumption of no unmeasured confounding. To account for weighting
325 the population (essentially multiplying observations by the weight coefficient) robust standard error
326 estimators will be used (Hernan & Robins, 2020).

327 The distributions of baseline covariates before and after weighting was compared between

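### Robust errors are tied only to weighting, not to the patient, so record-level use would overstate precision for the non-initiator arm and the per-protocol hazard ratio

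*Protocol*

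**What the plan says.** **Repeat entry.** Protocol section 4.5 states that "a patient may participate with several treatment episodes - and consequently index-dates" are possible. In its worked example of a man treated again after 15 months, "Therefore, this patient will enter the study twice and contribute with two" episodes. Each entry has its own follow-up: "Patients will be followed-up from index-date up to maximum one year".

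**Non-initiators.** Section 4.6 says: "Non-initiator comparators will be randomly sampled and selected on each date of the" recruitment period on which an esomeprazole or omeprazole initiator starts, matched on birth year. It gives no sampling ratio, no replacement rule and no limit per man. The definition looks only backwards: a non-initiator did "not have a recorded PPIs or H2RA prescription within 12 months before index-date or on index" date. Starting treatment later does not disqualify him.

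**Main analysis.** Box 2 gives the contrast as "Intention to treat effect, i.e., patients were followed up irrespective of treatment change (main analysis"). A non-initiator who starts treatment therefore stays in his arm.

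**Variance.** Section 4.7.3 gives one reason for robust errors, the weighting: "the population (essentially multiplying observations by the weight coefficient) robust standard error" estimators are to be used. The weights are also defined per observation. Clustering by patient appears nowhere in the protocol.

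**The concern.** The design lets records share a man, and often share his event. If he is drawn as a non-initiator three times within a year and then has a sexual dysfunction (SD) code, that one event enters three records. If he starts omeprazole during an open non-initiator year, his later event can count in both arms. A sandwich variance computed per record treats these copies as independent, and the reason given in section 4.7.3 does not cover this dependence.

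What is at stake is the stated precision of the non-initiator comparison. The protocol relies on this comparator for the background risk because lansoprazole and the H2RAs already list impotence as a side effect.

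**Working it through.** The plan gives no event count, power or interval width (section 4.7.5 sets no sample size), so there is no figure to reproduce.

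**Inputs from the protocol:** up to one year of follow-up per record; a washout of at least 365 days for active entries; prior SD excludes; non-initiators drawn on each initiation date.

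**Assumed, because not stated:** initiation rate q = 0.05 to 0.30 per eligible man-year; r = 1 to 10 non-initiators per initiator; SD rate 2 per 100 person-years; redraws allowed across dates.

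**Step 1. Non-initiator arm alone.** An eligible man is drawn about L = q × r times a year, and each record stays open for up to a year. The number of copies K of an event is then roughly Poisson with mean L. Variance inflation is E[K²]/E[K] = (L + L²)/L = 1 + L.

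**Step 2. Main intention-to-treat hazard ratio.** Let E be the initiator events, so that non-initiator records hold about rE.
- Record-level variance of the log ratio: 1/E + 1/(rE) = (1 + 1/r)/E.
- Overlap makes the second term (1 + qr)/(rE), which adds q/E.
- An initiator's event at time u in his year also falls in any non-initiator record drawn in the 1 − u years before he started. On average that is qr/2 copies. The covariance is E × (qr/2)/(E × rE) = q/(2E). It enters twice with a negative sign, so it removes q/E.
- The two effects cancel.

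**Step 3. Per-protocol hazard ratio.** Censoring at crossover (section 4.7.4) removes the both-arm overlap, so the covariance disappears. The variance is (1 + 1/r + q)/E, and the clustered-to-record SE ratio is √(1 + qr/(1 + r)).

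**Step 4. Simulation.** 6,000 men, five years of recruitment, one-year follow-up, 500 to 600 replicates, with a rate ratio standing in for the Cox hazard ratio.

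| q, r | Non-initiator arm, SE ratio: formula / simulated | ITT HR, SE: record / clustered | Per-protocol HR, SE: record / clustered (ratio; formula) |
|---|---|---|---|
| 0.05, 1 | √1.05 = 1.02 / √1.04 = 1.02 | 0.2804 / 0.2804 | 0.2802 / 0.2833 (1.01; 1.01) |
| 0.15, 4 | √1.60 = 1.26 / √1.54 = 1.24 | 0.1312 / 0.1313 | 0.1317 / 0.1391 (1.06; 1.06) |
| 0.30, 4 | √2.20 = 1.48 / √2.02 = 1.42 | 0.0983 / 0.0983 | 0.1001 / 0.1113 (1.11; 1.11) |
| 0.30, 10 | √4.00 = 2.00 / √3.55 = 1.88 | 0.0926 / 0.0925 | not simulated (formula 1.13) |

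- The ITT agreement also held with a hazard ratio of 1.5 (0.1120 against 0.1119) and with weighting for unequal initiation propensity (0.1567 against 0.1566).
- For the non-initiator arm alone, a second simulation with 8,000 men gave record-level 95% coverage of about 86–88% at q = 0.15, r = 4 and 67–73% at q = 0.30, r = 10.
- For the per-protocol ratio at q = 0.30, r = 4, coverage was 92.8% per record and 95.2% clustered.

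**Step 5. When the ITT cancellation fails.** Step 2 needs initiators who could have been drawn before they started. If they could not, for example because the indication was first recorded just before the prescription, the covariance is lost. Simulated ITT SE ratios were then 1.01 to 1.13. At q = 0.1 to 0.2 and r = 4, with half or all initiators outside the samplable pool, they were 1.02 to 1.05.

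**Step 6. Active comparators.** A 365-day washout with one-year follow-up means that two active entries of one man do not overlap, and a man with SD cannot re-enter. Each event counts once, so record-level and clustered errors should differ little.

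**The case against.** **Silence is not error.** Robust estimators do not exclude aggregation by patient, and an analysis plan that is not shown may name the cluster. This stands in part: the wording is incomplete, not proven wrong. But the protocol itself creates the dependence, chooses the estimator and gives a reason that leaves the dependence out. A programmer following section 4.7.3 literally could run a record-level sandwich.

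**No intervals are promised for rates or cumulative incidence.** Correct: section 4.7.3 describes only how the estimates are presented. The arm-level point therefore applies to any interval that is reported.

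**The size is assumed.** Also correct. Without the sampling ratio, the redraw rule and the initiation rate, only ranges can be given.

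**The stronger reading.** A reader might infer that overlap and both-arm membership together make the main hazard ratio against non-initiators too precise, so that chance could pass for a signal. The documents do not support this. Under intention-to-treat the two features act in opposite directions and cancel when initiators come from the samplable pool. Nor do the arm-level ratios carry over to the hazard ratio: per record, the non-initiator arm supplies only (1/r)/(1 + 1/r) = 1/(1 + r) of the log-ratio variance, one fifth at r = 4.

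**Conclusion.** The point holds as a gap in the variance specification, with uneven consequences if the robust variance is applied per record:

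- **Non-initiator rate and cumulative incidence:** the correct SE is about 1.02 to 1.9 times the record-level SE.
- **Per-protocol hazard ratio against non-initiators:** about 1% to 11% larger in the scenarios simulated.
- **Main ITT hazard ratio against non-initiators:** from no change to about 13% larger, depending on whether initiators could have been sampled beforehand. The protocol does not show which case applies.
- **Active-comparator hazard ratios:** little affected.

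These ranges rest on the assumed q, r and SD rate, on redraws being allowed, and on a rate ratio as proxy for the Cox model. Patient-level variance is valid in every scenario examined. For the ITT ratio, record-level variance is adequate only when the cancellation holds.

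**What to change.** In section 4.7.3, state that the robust variance of every weighted Cox model is aggregated by patient identifier across all episodes and arms. State also that any interval for a rate or cumulative incidence uses a patient-level bootstrap (resampling men with all their records) or an equivalent method. Apply the same rule to the per-protocol analyses in section 4.7.4.

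The cost is one option in the Cox procedure plus a bootstrap. Intervals for the non-initiator arm and the per-protocol hazard ratio become wider; the main ITT interval changes little or not at all if initiators come from the samplable pool. There is no need to bar a man from being drawn again once the variance is clustered. Stating the sampling ratio and the redraw rule in section 4.6 would let readers judge the size of the effect.

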328 esomeprazole and the other treatment arms by calculating and plotting standardized mean differences
329 (SMD), with a SMD of <10 used to determine appropriate covariate balance. For each variable, the
330 SMD was the difference in mean (for continuous variables) or proportion (for binary variables) between
331 each treatment arms and the entire study population (which is the target population in the ATE to
332 which the composition of covariates distribution in each treatment arm is standardized), divided by the
333 study population standard deviation of the variable. (McCaffrey et al., 2013)

334

335 **Intention-to-treat (ITT) analysis**

336 The ITT approach chosen for the main analysis will involve following patients from the date of study
337 treatment initiation (i.e., index date) until the earliest of any of the following: first outcome event date,
338 loss to follow-up (e.g., transfer out date from the general practice in IMRD or end of continuous
339 observation of the patient by the practice in IQVIA™ DA Germany, or date of last data collection from
340 the practice), date of death (only available in IMRD) or the end of the study. Consequently, outcome
341 events will be attributed to the baseline treatment regardless of treatment change during follow-up.
342 Moreover, it will be assumed that intercurrent events that may occur during follow-up are independent
343 of the risk of the outcome (i.e., the risk of experiencing the outcome among individuals remaining in
344 the analysis over the course of follow-up is representative of the risk among censored individuals).

345

346 **Incidence rates (IRs)**

347 IRs will be calculated as the number of events occurring during follow-up divided by the total person-
348 time in each treatment-arm. IRs will be presented as number of events per 100 person-years.

349

350 **Cumulative incidence (Incidence proportion)**

351 Survival (i.e., the proportion of the patients included at baseline who have not yet experienced a
352 sexual dysfunction event) over the course of follow-up will be estimated by treatment arm using the
353 Kaplan-Meier method. (Bland & Altman, 1998) The cumulative incidence will be calculated as the
354 complement of survival (i.e., the proportion of the patients included at baseline who have experienced
355 a sexual dysfunction event) at each follow-up time and will be presented as number of events per 100
356 patients.

357

358 **Cox proportional hazards model**

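### The balance limit of SMD below 10 is set in standard-deviation units, so as written it would practically never flag imbalance; the reference group for the SMD also needs reconciling

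*Protocol*

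**What the plan says.** The IPTW part of Section 4.7.3 (Main statistical analysis) makes four statements that bear on this point.

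- **Estimand:** "Using IPTW, the average treatment effect (ATE) in the entire study population will be estimated".
- **After weighting:** "All analyses will then be conducted in the re-weighted population without additional" confounder adjustment.
- **Balance check and limit:** the comparison is between "esomeprazole and the other treatment arms by calculating and plotting standardized mean differences", "with a SMD of <10 used to determine appropriate covariate balance".
- **Definition:** the "SMD was the difference in mean (for continuous variables) or proportion (for binary variables) between" "each treatment arms and the entire study population (which is the target population in the ATE to" which each arm's covariate mix is standardised), divided by the "study population standard deviation of the variable".

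No other balance limit appears in the protocol, and no percent scale is mentioned. Section 3 and Table 2 make omeprazole a second target treatment with its own set of comparators.

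**The concern.** An SMD defined as a difference over a standard deviation is a number of standard deviations. On that scale a limit of 10 asks whether an arm's mean lies ten standard deviations from the population mean, which real covariates almost never approach. A weighting model that had failed outright would still meet the stated criterion.

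This matters because the study is not randomised, plans to adjust for more than 50 potential confounders (Section 4.9), and puts that adjustment entirely in the weights.

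A second, smaller difficulty is that two adjacent sentences describe different contrasts. One sets esomeprazole against the other arms; the other sets each arm against everyone. The hazard ratios compare arm with arm.

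**Working it through.** The limit is a chosen rule, so there is no figure of the plan's to reproduce. The check applies the protocol's own definition and asks what could breach the limit.

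**1. Definition.** SMD = (arm mean or proportion − population mean or proportion) / population SD. For a binary covariate with population prevalence p and arm proportion a, SMD = (a − p) / √(p(1 − p)).

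**2. Largest high-side value for a binary covariate.** Setting a = 1 gives √((1 − p)/p). The prevalences are illustrative, as the protocol gives none.

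| Population prevalence | Largest SMD | Below 10? |
|---|---|---|
| 50% | √1 = 1.0 | yes |
| 20% | √4 = 2.0 | yes |
| 10% | √9 = 3.0 | yes |
| 5% | √19 = 4.36 | yes |
| 1% | √99 = 9.95 | yes |

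The maximum equals 10 when (1 − p)/p = 100, that is p = 1/101 = 0.99%. Just below that prevalence, nearly every patient in the arm must carry the covariate for the rule to flag it. At p = 0.5% the arm proportion would have to reach 0.005 + 10 × √(0.005 × 0.995) = 0.71.

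**3. Bound by arm size, before weighting.** For an arm that makes up share s of the population, |SMD| cannot exceed √((1 − s)/s), whatever the covariate: 1.0 at a 50% share, 3.0 at 10% and 9.95 at 1%. It reaches 10 only when the arm is 1/101 of the population or less and completely separated from the rest.

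**4. Continuous covariate.** With an assumed age SD of 10 to 20 years, the limit tolerates an age difference of 10 × 10 = 100 to 10 × 20 = 200 years.

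**5. The same rule at 0.10.** The written limit is 10/0.10 = 100 times looser. At 0.10, age is flagged at a difference of 1 to 2 years under the same assumed SDs. A covariate at 20% in the population has SD √(0.2 × 0.8) = 0.4, so it is flagged once an arm reaches 20% + 0.1 × 40 points = 24% or falls to 16%.

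**6. Effect of the reference group.** Two arms just inside those limits on opposite sides, near 24% and 16%, both pass. They differ from each other by 0.08/0.4 = 0.20 SD. The worst-case gap between contrasted arms is therefore twice the arm-versus-population limit.

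**The case against.** The strongest reply is that this is a typographical slip. A reader used to SMDs would take 10 to mean 10%, the SMDs are to be plotted before and after weighting so that gross imbalance would be visible, and the limit does not enter the weights, hazard ratios or standard errors. All of that is fair, and it makes the correction easy. It does not make the written rule work, and a prespecified criterion should not depend on the reader guessing its unit.

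Four stronger readings are tempting and are not supported.

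- **That the rule can never flag anything.** A covariate below about 1% prevalence that is heavily concentrated in one arm could exceed 10. The listed confounders include drugs that may be that rare, although no prevalences are given.
- **That measuring each arm against the whole population is an error.** The protocol states the reason, that the population is the ATE target, and cites a tutorial on propensity scores for multiple treatments. The 0.20 figure is a worst case. In an unweighted two-arm split of 90:10, for example, the smaller arm's gap to the population is 0.9 of the pairwise gap, so it would be flagged at a pairwise difference of 0.10/0.9 = 0.11.
- **That omeprazole goes unchecked.** The formula covers every arm, and omeprazole is one of the arms that esomeprazole is compared with. What is missing is only an announced pairwise check of omeprazole against its other comparators.
- **That the limit is the only protection against measured confounding.** Baseline description, the SMD plots, active comparators, and matching of non-initiators on birth year and index date all contribute. The limit is the only numerical balance criterion, which is a narrower statement.

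**Conclusion.** The limit is wrong as written and should be corrected. Under the protocol's own definition it tolerates ten standard deviations, 100 times the 0.10 that was probably meant, and practically no imbalance would breach it. The binary bounds follow from the definition alone; the covariate prevalences and the age SDs are illustrative assumptions. That 0.10 (10%) was intended is an inference, because the protocol does not say so.

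The mismatch over the reference group is a matter of wording and completeness. The arm-versus-population SMD suits the ATE, but it does not directly show balance between the arms whose hazards are compared. A reader should not infer that the planned estimates are invalid: the weights and models are unaffected, and what fails is the stated test of whether the weighting has worked.

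**What to change.** In the IPTW part of Section 4.7.3:

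1. State the criterion as an absolute weighted SMD below 0.10 (10%).
2. Reconcile the two sentences so that the reference group is named consistently, keeping the arm-versus-population SMD for the ATE.
3. Add pairwise SMDs for each contrast of esomeprazole and of omeprazole with its comparators.
4. Say what follows a failure: respecify the propensity model before outcomes are analysed. Adding the failing covariates to the Cox model contrast by contrast is less suitable. It conflicts with the plan of no further adjustment, and because hazard ratios are non-collapsible it could replace a marginal hazard ratio with conditional ones that differ between contrasts.

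The cost is a change of wording and a few more rows in the balance table. Some covariates may fail a working limit and require the propensity model to be respecified.
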